3.3.4 Plasma 765IGF Level and 765IGF-MTX toxicity/response

3.3.5 Plasma and whole blood IGF-1R level and 765IGF-MTX Toxicity/Response

3.3.6 Assess formation of antibodies against 765IGF-MTX

3.3.7 Assess formation of neutralizing antibodies

3.3.8 IGF-1R expression level in diseased tissue in bone marrow, as measured by IHC, and flow cytometry, and in blood cells as measured by flow cytometry.

4. Overall Design and Study Plan

This pilot study will evaluate the safety and clinical benefit of 765IGF-MTX in patients with advanced, previously treated MDS, CMML or O-AML. 765IGF-MTX is administered as an IV infusion over 1.5 hours on days 1, 8 and 15 of a 28 day cycle. Treatment continues until disease progression, unacceptable toxicity, or patient refusal. Assessment of response will be confirmed with bone marrow studies performed at the end of cycle 2, and every 8 weeks +/- 7 days (2 cycles) thereafter up to the end of cycle 6, and at physician's discretion thereafter.

- Dose Finding Component: Up to 5 dose levels will be tested (refer to schema on page 6). The maximum tolerated dose (MTD) will be determined using the modified toxicity probability interval design with dose limiting toxicity (DLT) estimated at 0.33.

Our modification involves using cohorts of size 1 for the initial doses, which allows rapid escalation through the initial dose levels, and expanding to cohorts of size 3 once any grade 2 or higher toxicity is observed that is considered related to study drug (with the exception of alopecia, nausea, or diarrhea). Additional patient cohorts will not be enrolled until 1 of 1 (with no grade 2 toxicity), 3 of 3, 5 of 6, or 7 of 9 patients at the current dose level complete all planned treatment for cycle 1 (defined as 3 doses of 765IGF-MTX without DLT and are able to start cycle 2 with no more than a 2 week delay. At the discretion of the principal investigator, intra-patient dose escalation between cycles is also allowed but only after 2 cycles at one dose level and confirmation of safety in at least 3 patients treated at the higher dose level.

If none of the dose levels are acceptable at study completion, an optimal dose level will not be identified and the drug does not warrant further investigation.

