- Maximum Tolerated Dose (MTD) Cohort with pharmacokinetics (PKs) and pharmacodynamics (PD): The MTD will be defined as the highest dose associated with DLT in less than 33% of patients treated. Once the MTD is determined, enrollment will continue until 9 patients total are accrued at the MTD. For this group, pharmacokinetics will be performed on at least 3 patients before and for up to 48 hours after drug administration on days 1 and 15 of cycle 1. Pharmacodynamic samples will be assessed on day 1 of cycle 1, and days 1 and 15 of cycle 2 before the infusion of 756IGF-MTX, and one sample will also be drawn within the fourth week of each treatment cycle.

If none of the dose levels are acceptable at study completion, an optimal dose level will not be identified and the drug does not warrant further investigation.

Dose limiting toxicity (DLT) for a patient is defined as one of the following events occurring during cycle 1:

- Grade 4 or greater treatment related hematologic toxicity for > 7 days during the first cycle (28 days) of therapy
- Grade 3 or greater treatment related clinical non-hematological toxicity (excluding \geq grade 3 nausea, vomiting, or diarrhea without maximal medical intervention and/or prophylaxis) during the first cycle (28 days) of therapy
- Febrile neutropenia during the first cycle (28 days) of therapy

- Platelets less than $10 \times 10^9/L$ with clinically significant bleeding during the first cycle (28 days) of therapy

Additional patient cohorts will not be enrolled until 1 of 1 (with no grade 2 toxicity), 3 of 3, 5 of 6, or 7 of 9 patients at the current dose level complete all planned treatment for cycle 1 (defined as 3 doses of 765IGF-MTX without DLT and are able to start cycle 2 with no more than a 2 week delay).

The MTD will be defined as a dose level at which fewer than 33% of patients treated experience a DLT.

A minimum of 9 patients are to be treated at the MTD to assure safety and 765IGF-MTX based pharmacokinetics will be performed on at least 3 patients in total.

Pharmacokinetics will be performed before and for up to 24 hours after drug administration on days 1 (for 24 hrs) and 15 (for 24 hrs) of cycle 1. Pharmacodynamic samples will be assessed pre-dosing on day 1 of cycle 1, pre-dosing on days 1 and 15 of cycle 2, and pre-dosing on day 15 of cycles 4 and 6.

5. Selection of Patients

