7.2. Dose Modifications

7.2.1. Start of a New Cycle

Toxicity and adverse will be classified according to NCI's Common Terminology Criteria for Adverse Events Version 4.0 (CTCAE). A copy of the CTCAE can be downloaded from the CTEP home page:

(http://ctep.cancer.gov/protocolDevelopment/electronic_applications/ctc.htm#ctc_40).

Assessment of clinical benefit will be performed by investigators at the end of cycle 1 and confirmed with bone marrow studies as per MDS, CMML or O-AML specific response criteria (Appendices I and II) done at the end of cycles #2, 4, and 6 (i.e., at 8, 16, and 24 weeks, each +/- 7 days) and at the discretion of the physician thereafter.

A new treatment cycle will only be initiated when all of the following conditions are met:

- non- hematologic treatment related toxicities have improved to \leq Grade 1 (CTCAE v.4.0) or to the patient's baseline values (except alopecia)
- Platelets per 7.1 (platelets $> 10 \times 10^9/L$)

If blood counts are below this threshold at the 4 week point, blood work is to be repeated weekly until counts are at an acceptable level. Treatment will be restarted with appropriate dose modifications provided CTCAE hematologic grade ≥ 4 is not prolonged for more than 6 weeks in the absence of persistent disease. If treatment is unable to restart within 4 weeks of the planned treatment date, the patient will be permanently discontinued from study therapy.

CTCAE v.4.0 Adverse Effects Terms & Descriptions (see below for allergic reaction/hypersensitivity)	765IGF-MTX Dose Modifications (for treatment-related toxicities deemed clinically significant)
Any persistent (>4 weeks) grade 2 treatment-related non-hematologic toxicity	Drop to next lower dose level or discontinue treatment.
Grade 4 or greater treatment-related hematological toxicity for >7 days.	Drop to next lower dose level or discontinue treatment.
Grade 3 or greater treatment-related clinical non-hematological toxicity, excluding grade 3 nausea, vomiting, or diarrhea without maximal medical intervention and/or prophylaxis.	Drop to next lower dose level or discontinue treatment.
Febrile neutropenia.	Drop to next lower dose level or discontinue treatment.
Platelets less than $10 \times 10^9/L$	Wait to improve and then drop to next lower dose level or discontinue treatment.

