CTCAE Grade 1 Allergic Reaction/Hypersensitivity: (Transient flushing or rash, drug fever $< 38^{\circ}C$): Supervise without further treatment for allergic reaction/hypersensitivity.

CTCAE Grade 2 Allergic Reaction/Hypersensitivity: (Rash, flushing, dyspnea, urticaria, drug fever greater than or equal to $38^{\circ}C$) and/or asymptomatic bronchospasm: Interrupt the infusion. If symptoms abate, attempt re-infusion at a slower rate. If the symptoms recur,

discontinue infusion and follow for recurrent allergic reaction/hypersensitivity in the next paragraph.

Recurrent CTCAE Grade 2 or CTCAE Grade 3 or 4 Allergic Reaction/Hypersensitivity:

Stop the infusion. Administer additional doses of H1 and H2 blockers intravenously. Administer IV steroids and consider epinephrine and bronchodilators as clinically indicated.

CTCAE Grade 3 or 4 Allergic Reaction/Hypersensitivity: Stop the infusion. Administer additional doses of H1 and H2 blockers intravenously. Administer IV steroids and consider epinephrine and bronchodilators as clinically indicated. Will be permanently discontinued from study treatment.

Prior to re-challenge of Grade 2 allergic reaction/HSR and with all subsequent cycles:

The following prophylactic premedications are recommended for future infusions: give both an H1 and H2 blocker intravenously plus dexamethasone 20 mg (orally or intravenously) within 30 to 60 minutes before 765IGF-MTX infusion. Dexamethasone could be used at the investigator's discretion in subsequent cycles for recurrent (i.e. occurring despite slowing infusion as discussed above) Grade 2 reactions but would not be mandated.

An appropriate resuscitation plan should be in place and a physician readily available during the period of drug administration. If treatment delay necessitates a period longer than 4 weeks, treatment is stopped and the subject is discontinued from the study.

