13.2.3. Safety Endpoints

Incidence rates of treatment-emergent adverse events will be summarized within treatment group at the MedDRA preferred term and primary system organ class levels. Similar summaries will be made for subsets of AEs such as (1) those judged by the Investigator to be related to study treatment, and (2) serious adverse events (SAEs). Other routine safety assessments (e.g., clinical laboratory parameters, ECG parameters, and vital signs) will be summarized by standard deviation, median, minimum and maximum observed values and changes from baseline values. NCI-CTCAE severity grades for laboratory parameters and other endpoints measured on an ordinal categorical scale may be summarized using shift tables (a two-way frequency table pairing baseline value with the most extreme post-baseline result).

Additional exploratory analyses may be performed to assist the sponsor in planning future studies.

13.3. Analysis plan for primary objective:

The primary objective is to determine safety and tolerability of 765IGF-MTX by evaluation of toxicity for the treatment of advanced, previously treated hematologic malignancies. Preliminary information will be collected for treatment related toxicity and tolerance. Toxicity will be graded using the NCI's Common Terminology Criteria for Adverse Events version 4 (CTCAE v.4.0). Treatment tolerance will be based on the number of dose-limiting toxicities, treatment delays and dose reductions. Information will be presented in a tabular and descriptive manner.

13.4 Analysis plan for secondary objectives:

13.4.1 Objective Response Rate, Relapse-Free Survival, Overall Survival and Cumulative Incidence of Relapse; descriptive statistics will be used to describe clinical benefit measured by the above parameters.

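### Section 13.3 leaves permanent discontinuation for toxicity out of the tolerance measure, so after cycle 1 a direct stop adds nothing while a dose reduction for the same event is counted

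*Combined protocol and SAP*

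**What the plan says.** The primary objective (Section 2.1) is safety and tolerability, including the MTD. Section 13.3 grades toxicity by CTCAE and then defines the second half of the objective: "Treatment tolerance will be based on the number of dose-limiting toxicities, treatment delays and dose reductions". Results are to be tabulated and described; no score or test is specified.

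The rules that feed those three counts are elsewhere:

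- **DLT window, Section 4:** "Dose limiting toxicity (DLT) for a patient is defined as one of the following events occurring during cycle 1". Nothing after cycle 1 can be a DLT.
- **Length of treatment, Section 4:** "Treatment continues until disease progression, unacceptable toxicity, or patient refusal". Treatment is open-ended, and after two cycles a patient may be escalated to a higher dose level.
- **Dose-modification table, Section 7.2.1:** for persistent grade 2 non-hematologic toxicity, prolonged grade 4 hematologic toxicity, grade 3 or higher non-hematologic toxicity and febrile neutropenia, the entry is "Drop to next lower dose level or discontinue treatment". Low platelets carry the same choice after a wait.
- **Grade 3 or 4 hypersensitivity, Section 7.2.1:** "Will be permanently discontinued from study treatment".
- **Failed restart, Section 7.2.1:** "If treatment is unable to restart within 4 weeks of the planned treatment date, the patient will be permanently discontinued from study therapy".
- **Adverse event tables, Section 13.2.3:** "Incidence rates of treatment-emergent adverse events will be summarized within treatment group at the MedDRA preferred term and primary system organ class levels". The subsets given as examples are related events and serious events.

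**The concern.** Stopping treatment because of toxicity is the plainest sign that a patient could not tolerate the drug, yet it is not one of the three counts. After cycle 1 the measure depends on which permitted action the physician takes rather than on how the patient fared. A reduction is recorded as a tolerance event; an immediate stop for the same toxicity is not. At dose level 1 (0.20 µeq/kg) the schema lists no lower level, so a reduction cannot be recorded there.

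The case is foreseeable. The protocol reports anaphylactoid reactions in dogs (Section 1.2.1) and a possible allergic reaction in one earlier patient (Section 7.1.1). It also says that anti-drug antibodies, though thought unlikely, would raise the risk of anaphylaxis (Section 9.6). Antibodies cannot be present at the first dose (Section 9.1.3), so a reaction of that kind would come later, possibly after the DLT window has closed.

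What is at stake is the tolerability that the trial reports for each dose level.

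**Working it through.** The plan gives no figure for the tolerance measure, so there is none to reproduce. The check has three steps.

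**1. What each route adds to the three counts.** Inputs are the DLT definition in Section 4, the rules in Section 7.2.1 and the list in Section 13.3.

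| Route | In cycle 1 | After cycle 1 |
|---|---|---|
| Related grade 3+ non-hematologic toxicity, dose reduced | counted (DLT) | counted (reduction) |
| Same toxicity, treatment stopped directly | counted (DLT) | not counted |
| Related grade 3 or 4 hypersensitivity, mandatory stop | counted (DLT) | not counted |
| Stopped because treatment could not restart within 4 weeks | not applicable | countable (delay) |

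The gap is the direct stop after cycle 1. At dose level 1 the first route has no listed lower level, which leaves stopping as the only one of the table's two actions.

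**2. Same toxicity, different action.** Let *k* of *n* patients have one late toxicity each, and let *s* of them be stopped directly with no earlier counted event. The measure records *k* − *s*. Take *n* = 9, the planned total at the MTD, and *k* = 3 (assumed):

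- *s* = 0: 3/9 = 33%
- *s* = 1: 2/9 = 22%
- *s* = 2: 1/9 = 11%
- *s* = 3: 0/9 = 0%

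With discontinuation counted, the result is 3/9 for every *s*.

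**3. Can a more toxic level show the lower count?** This is an illustration; the rates are assumptions, not figures from the documents. Level A has 30% late toxicity, all managed by reduction. Level B has 60%, all ending in a stop. A share *f* of B's stops follows a delay or reduction that was counted. With nine patients at each level:

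- A: expected count 9 × 0.30 = 2.7
- B: expected count 9 × 0.60 × *f* = 5.4*f*

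The last column treats the two counts as independent binomials, Bin(9, 0.30) and Bin(9, 0.60*f*).

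| *f* | B expected | Chance that B's count is below A's |
|---|---|---|
| 0 | 0 | 96% |
| 0.25 | 1.35 | 69% |
| 0.5 | 2.7 | 40% |
| 1 | 5.4 | 6% |

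The expected order reverses only when *f* is below 0.30/0.60 = 0.5. With rates of 20% and 50% the threshold is 0.20/0.50 = 0.4; with one third and two thirds it is 0.5. If stops are counted, B's expected count is 5.4 against 2.7 for A, whatever *f* is.

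**The case against.** The strongest reply is that one sentence is not the whole primary analysis. The primary endpoint (Section 3.1) is adverse events by CTCAE. Section 11.2 requires related events of grade 2 and above to be documented, and Section 13.2.3 tabulates treatment-emergent, related and serious events. Toxicity that ends treatment in cycle 2 appears there whichever action was taken. This stands, but only in part: those tables show that an event occurred, not that it ended treatment. The list of subsets is open, but events leading to discontinuation are not named, and the descriptors required in Section 11.2 do not include action taken.

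Section 13 also calls itself an overview and defers details to a full SAP. That SAP may add a discontinuation table. It is not among the documents, however, and Section 13.3 as written states a specific list that leaves discontinuation out.

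A reader might go further and infer that every patient who stops for toxicity after cycle 1 scores zero, so that a dose toxic enough to make patients stop will look better than one at which they are reduced. The documents do not support that:

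- A patient stopped after a failed restart, or after waiting for platelets to recover, can already have a counted delay.
- No composite score is planned, and no rule ranks dose levels on this count. The MTD uses the DLT rate.
- Early stops already weigh on escalation, because Section 4 requires enough patients to complete three cycle 1 doses without DLT and to start cycle 2 on time.
- Reversal depends on *f*, which the documents do not give.

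Nor is the measure without a denominator: Section 13.2 generally provides numbers and percentages of patients by dose level, with confidence intervals.

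**Conclusion.** The point holds as an omission in a stated definition. After cycle 1, a patient stopped directly for toxicity adds nothing to the tolerance measure for that event, while a patient reduced for the same event does. The tolerance summary can therefore understate intolerance, on one half of the primary objective, and no table planned in Section 13 shows that toxicity ended treatment.

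The shortfall equals the number of direct late stops without an earlier counted event. In the nine-patient example it ranges from 0 to 3 patients, or 0 to 33 percentage points. The upper end assumes that all three affected patients are stopped directly. A reversal between dose levels is possible but not established, and it would concern this summary only; dose selection by the MTD rule is unaffected.

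**What to change.** In Section 13.3, or in the full SAP before database lock:

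1. Add the number and percentage of patients who permanently discontinue for treatment-related toxicity in any cycle, by dose level.
2. Report, by dose level, the number of patients with any of DLT, toxicity-related delay, dose reduction or discontinuation, each patient counted once.

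In Section 13.2.3, name adverse events leading to discontinuation as a subset to be tabulated.

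Because escalation within a patient is allowed, say whether a stop is attributed to the assigned level or to the level in force at the time. Relative dose intensity and rates per cycle due are optional. Both would need extra rules, because day 8 and 15 visits are discretionary from cycle 3 and patients may be escalated.

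The cost is one more table and a check that the case report form records why treatment stopped. The explicit requirement to record a removal reason (Section 6.2) covers patients who never start treatment. Reported tolerability may look less favourable. No clinical rule changes.

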13.5.6 Antibody formation against 765IGF-MTX: Serum samples from before infusion on D1 of cycle 1, and before infusion on D1 and D15 of cycle 2 and day 15 of cycles 4 and 6 will be collected and analyzed for anti-765IGF-MTX antibodies. A descriptive analysis will be done correlating anti-765IGF-MTX antibody presence or levels with clinical response and toxicity.

13.5.7 Neutralizing antibodies and 765IGF-MTX toxicity/response: Serum samples from before infusion on D1 of cycle 1 and before infusion on D1 and D15 of cycle 2 and D15 of cycles 4 and 6 will be collected for presence of neutralizing antibodies. A descriptive analysis will be done correlating presence or levels of neutralizing antibodies with clinical response and toxicity.

13.5.8 IGF-1R expression level in bone marrow biopsies via IHC and flow cytometry and IGF-1R expression level in blood cells by flow cytometry: IGF-1R expression at baseline will be performed on paraffin-embedded fixed bone marrow aspirates by Quest Diagnostics by IHC and IGF-1R expression at baseline will be performed on fresh viable bone marrow aspirates and fresh whole blood by Charles River, Inc. by flow cytometry. If sample sizes are small and heterogeneous, clinical responses will be reported by dose and disease (MDS, CMML, or O-AML) type

14 Conduct of the Study

14.1 Good Clinical Practice

The study will be conducted in accordance with the appropriate regulatory requirement(s). Essential clinical documents will be maintained to demonstrate the validity of the study and the integrity of the data collected. Master files should be established at the beginning of the study, maintained for the duration of the study and retained according to the appropriate regulations.

Appendix I – Response Criteria for Acute Leukemia

Acute Myeloid Leukemia⁴⁵

Table 5. Response criteria in AML

Category	Definition
Complete remission (CR)*	Bone marrow blasts < 5%; absence of blasts with Auer rods; absence of extramedullary disease; absolute neutrophil count $> 1.0 \times 10^9/L$ (1000/ μ L); platelet count $> 100 \times 10^9/L$ (100 000/ μ L); independence of red cell transfusions
CR with incomplete recovery (CRI)†	All CR criteria except for residual neutropenia ($< 1.0 \times 10^9/L$ [1000/ μ L]) or thrombocytopenia ($< 100 \times 10^9/L$ [100 000/ μ L])
Morphologic leukemia-free state‡	Bone marrow blasts < 5%; absence of blasts with Auer rods; absence of extramedullary disease; no hematologic recovery required
Partial remission (PR)	Relevant in the setting of phase 1 and 2 clinical trials only; all hematologic criteria of CR; decrease of bone marrow blast percentage to 5% to 25%; and decrease of pretreatment bone marrow blast percentage by at least 50%
Cytogenetic CR (CRC)§	Reversion to a normal karyotype at the time of morphologic CR (or CRI) in cases with an abnormal karyotype at the time of diagnosis; based on the evaluation of 20 metaphase cells from bone marrow
Molecular CR (CRM)¶	No standard definition; depends on molecular target
Treatment failure	
Resistant disease (RD)	Failure to achieve CR or CRI (general practice; phase 2/3 trials), or failure to achieve CR, CRI, or PR (phase 1 trials); only includes patients surviving ≥ 7 days following completion of initial treatment, with evidence of persistent leukemia by blood and/or bone marrow examination
Death in aplasia	Deaths occurring ≥ 7 days following completion of initial treatment while cytopenic; with an aplastic or hypoplastic bone marrow obtained within 7 days of death, without evidence of persistent leukemia
Death from indeterminate cause	Deaths occurring before completion of therapy, or < 7 days following its completion; or deaths occurring ≥ 7 days following completion of initial therapy with no blasts in the blood, but no bone marrow examination available
Relapse	Bone marrow blasts $\geq 5\%$; or reappearance of blasts in the blood; or development of extramedullary disease

Table 6. Outcome measures in AML

Category	Definition
Overall survival	Defined for all patients of a trial; measured from the date of entry into a study to the date of death from any cause; patients not known to have died at last follow-up are censored on the date they were last known to be alive
Relapse-free survival*	Defined only for patients achieving CR or CRI;‡ measured from the date of achievement of a remission until the date of relapse or death from any cause; patients not known to have relapsed or died at last follow-up are censored on the date they were last examined
Event-free survival	Defined for all patients of a trial; measured from the date of entry into a study to the date of induction treatment failure, or relapse from CR or CRI;‡ or death from any cause; patients not known to have any of these events are censored on the date they were last examined
Cumulative incidence of relapse (CIR)†	Defined for all patients achieving CR or CRI;‡ measured from the date of achievement of a remission until the date of relapse; patients not known to have relapsed are censored on the date they were last examined; patients who died without relapse are counted as a competing cause of failure

*Relapse-free and disease-free survival have been used with the same definition

†It is important to provide estimates of cumulative incidence of death (CID) as well, since just considering the results of CIR may be misleading if for instance CIR is lower for one group but CID is actually higher for that same group.

‡In studies where the criterion CRI is used, relapse-free survival should be defined for all patients achieving CR or CRI; for event-free survival, relapse should be considered from CR and CRI.

FAILURE - aplasia Aplasia: Patient survives \geq 7 days following completion of initial treatment course then dies while cytopenic, with the last post-induction bone marrow aplastic or hypoplastic (i.e. < 20% cellularity) and without leukemia blasts.

FAILURE - indeterminate Indeterminate: (a) Patient survives < 7 days after completion of initial treatment course; **or** (b) patient survives \geq 7 days following completion of initial treatment course then dies with no persistent leukemia in the peripheral smear but no post-induction bone marrow examination.

RELAPSE FROM CR Relapse: Reappearance of leukemia blasts in the peripheral blood; or > 5% blasts in the bone marrow not attributable to another cause (e.g., recovery of normal cells following chemotherapy-induced aplasia); or appearance or reappearance of extramedullary disease.

